Date: 2024-10-27 4 (48)

# Funding and research agreement

This is an academic design and financed pilot study. Participating sites will in this trial take own economic responsibilities in taking their own costs. For this purpose, a resource certificate is signed. The Corpuls3 defibrillators used in this trial are part of the participating sites standard equipment. Additional Corpuls1 defibrillators and CPR quality feed-back devices will be provided by the sponsor. A minor economical deal covering education, data management and defibrillation electrode pads used in the trial will be provided.

# List of used acronyms and abbreviations

Abbreviation	Term/Explanation
ACLS	Advanced Cardiac Life Support
ADE	Adverse Device Effect
A-L	Anterior - Lateral
A-P	Anterior - Posterior
AE	Adverse Event
CIP	Clinical Investigation Plan
CPC	Cerebral Performance Category
CPR	Cardiopulmonary Resuscitation
CRF	Case Report Form

Version No: 1.1

Date: 2024-10-27 8 (48)

DD	Device Deficiency
DSD	Double Sequential Defibrillation
DMC	Data Monitoring Committee
GCP	Good Clinical Practice
IB	Investigator's Brochure
IFU	Instructions for Use
ILCOR	International Liason Committee on Resuscitation
SS-EN ISO	Swedish Standard - European standard International
33-LN 130	Organization for Standardization
ITT	Intention-to-treat = including all data from all subjects who have
	participated in the clinical investigation
MDCG	Medical Device Coordination Group
mRS	Modified Rankin Scale
OHCA	Out-Of-Hospital Cardiac Arrest
	Per Protocol analysis = including only data from subjects who
PP	have completed the clinical investigation completely in
	accordance with the CIP, with no deviations from the CIP
ROSC	Return Of Spontaneous Circulation
SADE	Serious Adverse Device Effect
SAE	Serious Adverse Event
USADE	Unanticipated Serious Adverse Device Effect
VF	Ventricular Fibrillation
VT	Ventricular Tachycardia

Version No: 1.1

Date: 2024-10-27 9 (48)

## 1. Synopsis

Background and rationale and design:

**Background:** Out-of-hospital cardiac arrest (OHCA) affects about 270,000 individuals in Europe annually.[1] In OHCA, presenting with ventricular fibrillation (VF) or pulseless ventricular tachycardia (VT) amendable to defibrillation are among the strongest predictors of survival.[2] If defibrillation can be done successfully within the first 3-5 minutes survival can be as high as 70 %.[3] However, some patients in VT/VF do not respond to initial defibrillation, and survival decreases with number of defibrillations required to terminate VT/VF.[4]

In 2022, one prospective cluster randomized trial showed increased survival among OHCA patients in refractory VF using an alternative defibrillation strategy with either, switching to Anterior-Posterior defibrillation pad placements (A-P) or Double Sequential Defibrillation "DSD", (Using two defibrillators, one in the standard anterior-lateral position (A-L) and one in A-P position and defibrillation in rapid sequence) compared to standard defibrillation pad placement.[5] Refractory VF was defined as VF that persisted despite three consecutive defibrillations with defibrillation pads in the standard position.

These results prompted the International Liason Committee on Resuscitation (ILCOR) to release a statement of treatment recommendation on DSD in March 6, 2023. It suggested that "...either vector change or DSD may be considered for adults with cardiac arrest who remain in ventricular fibrillation or pulseless ventricular tachycardia despite three defibrillations (weak recommendation, low certainty of evidence)." [6]

Further, if DSD would be used it should be performed with a methodology similar to that described in the trial by Cheskes et al.

However, several questions remain. Knowledge gaps highlighted in the ILCOR statement included if the results from this one cluster randomized trial could be reproduced in any other setting. Further, since survival is inversely associated with the number of defibrillation shocks, if earlier application of DSD could lead to even higher

Version No: 1.1

Date: 2024-10-27 10 (48)

survival for patients not in refractory VF has never been studied.

**Study rationale:** In order to evaluate if an early DSD-strategy could benefit all patients with VT/VF after the first shock, including those not in refractory VF the Double D trial is designed. The first phase of the Double D trial is a pilot-study assessing feasibility and defibrillation safety, presented here. If DSD would prove to be superior to standard defibrillation in a broader cardiac arrest population, also among those not in refractory VF, this would have a large impact on how Advanced Cardiac Life Support (ACLS) should be performed.

**Design:** This is an academic, investigator initiated, openlabel pilot study with a randomized controlled trial (RCT) design and 3:1 allocation (3 DSD: 1 standard). Screening for inclusion will be performed in all cardiac arrests by participating EMS units where there are two study-specific defibrillators available on site (One (1) Corpuls3 + one (1) Corpuls3).

**Study population:** All OHCA patients (≥18 years) with VT/VF at rhythm analysis, at least one defibrillation performed in standard A-L position.

**P:** Adult patients, 18 years or older, with OHCA and a shockable rhythm (VT/VF) after ambulance arrival and at least one defibrillation in standard position

**I:** Application of a second defibrillator with pad-placement in the anterior-posterior (A-P) position as early as possible after the first shock and a double sequential defibrillation in the following rhythm analysis phase if the patient is still in VT/VF

**C:** Standard defibrillation electrode placement (A-L)

**O**: Assessment of feasibility in terms of inclusion, time to inclusion and randomization, adherence to protocol and safety in terms of adverse events and CPR quality.

The pilot study is conducted in the prehospital emergency medical services, i.e. ambulance organizations primary in Alingsås/Kungälv, Sahlgrenska, Gothenburg and Region Halland. Other areas/regions can be allocated later.

Version No: 1.1

Date: 2024-10-27 11 (48)

	The trial will be conducted by participating ambulance units attending OHCA's. These units will perform screening for inclusion, randomization, intervention or control treatment and initial follow up.
Investigational device:	Corpuls3
Number of subjects:	40
Inclusion criteria:	- OHCA patients with VT/VF and at least one (1) defibrillation performed in standard (A-L) position
Exclusion criteria:	

- Age < 18 years

- Obvious pregnancy

- Known preexisting Do Not Attempt Resuscitation order

Study objectives:	Primary objective: To evaluate feasibility and defibrillation safety in a randomized pilot trial, comparing the effect of a double defibrillation strategy, initiated as soon as possible after the first shock has been delivered, among all patients with Out of Hospital Cardiac arrest (OHCA) remaining in a shockable rhythm (VT/VF) after the first defibrillation. The results from this pilot trial will inform design of a larger multicenter survival study.
	Secondary objective: To provide a power-calculation for a larger survival study
	Safety objective: To asses safety of an early DSD strategy in terms of CPR quality and defibrillation performance.
Study endpoints:	Primary endpoints are defined as feasibility and safety measures as described below:
	Feasibility:  - Number of EMS defibrillations prior to randomization (target > 80% before third defibrillation)  - Among patients randomized to DSD, proportion that received DSD (target > 80%)  - Among patients randomized to standard, proportion that received DSD (target < 10%)

Version No: 1.1

Date: 2024-10-27 12 (48)

- Proportion of eligible patients included and randomized (target > 80%)

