#### Performing DSD within the Double-D trial:

In this trial all patients will be connected to corpuls3 with electrodes in standard A - L electrode position.

If another defibrillator (AED) is already attached to the patient at EMS arrival the EMS will remove the electrodes from the other defibrillator and attach cor-patch electrodes in standard A-L position and connect them to corpuls3 in all cases. This is all part of current routine practice.

If randomized to intervention, electrodes from a second defibrillator (corpuls3 or corpuls1) are placed in the anterior-posterior position during interruptions in chest compressions for ventilation, thus not interfering with the electrodes from the first defibrillator. Attachment of the second defibrillator electrodes shall be made as soon as possible after randomization.

Version No: 1.1

Date: 2024-10-27 17 (48)

If the patient has VT/VF at the subsequent rhythm analysis (every two minutes during CPR) both defibrillators are charged simultaneously during chest compressions and shocks from the two defibrillators are delivered with approximately 1 second delay from each other (A-L first, A -P second when possible) and CPR immediately resumed (DSD strategy). For all consecutive defibrillations a DSD strategy will be used if the patient remains in VT/VF, termination of resuscitation or decision to transfer the patient to hospital. The total shock pause (hands off interval where no compressions are performed) is recommended to be less than 5 seconds.

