## 5. Objectives and hypotheses of the clinical investigation

## 5.1. Objectives

## 5.2.1. **Primary objective**

The overall aim of this pilot study is to evaluate feasibility of a Randomized Controlled Trial comparing a strategy with DSD defibrillation as soon as possible to standard defibrillation in OHCA patients who remain in VT/VF after the first shock.

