## 6. Design of the clinical investigation

#### 6.1. General information

**Design:** This is an academic, investigator initiated, open-label pilot study with a randomized controlled trial (RCT) design and 3:1 allocation (3 DSD: 1 standard). Screening for inclusion will be performed in all cardiac arrests by participating EMS units where there are two study-specific defibrillators available on site (One (1) Corpuls3 + one (1) Corpuls3 *or* one (1) Corpuls1).

**Study population:** All adult OHCA patients (≥18 years) with VT/VF at rhythm analysis after the first defibrillation.

Version No: 1.1

Date: 2024-10-27 25 (48)

**Study setting:** The study is conducted in the prehospital emergency medical services, i.e. ambulance organizations. The trial will be conducted by participating ambulance units attending OHCA's staffed with special nurses. These units will perform screening for inclusion, randomization, intervention or control treatment and initial follow-up. All ambulance units in Sweden follow European resuscitation council (ERC) guidelines published in 2021 [4] and perform team training on an annual basis for high quality provision of ACLS care in OHCA.

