#### Feasibility:

- Number of EMS defibrillations prior to randomization (target > 80% before third defibrillation)
- Among patients randomized to DSD still in VF in the following rhythm analysis, proportion that received DSD (target > 80%)
- Among patients randomized to standard, proportion that received DSD (target < 10%)

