#### Intervention

If the patient is randomized to the intervention group, the ambulance crew team will apply the second defibrillator with electrodes placed in the A-P position as soon as possible. Defibrillation is performed by one person defibrillating both defibrillators in a sequential manner "Double Sequential Defibrillation" (DSD). All consecutive defibrillations will thereafter be performed with the DSD strategy until ROSC, termination of resuscitation or decision to move the patient to hospital.

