#### 8.1 Prehospital CRF1, Characteristics during the resuscitation phase

After completing the care of the patient, the study responsible EMS-unit will report a digital prehospital CRF. This is practically done by using and reading a study specific QR-code located on the back of the specific randomization envelope / sheet using a smart-phone. This will open a webpage automatic registration of time of registration and information to be filled in when opened.

Version No: 1.1

Date: 2024-10-27 33 (48)

The prehospital CRF will contain basic on-site information such as which ambulance that performed randomization, randomization study number, time and date of cardiac arrest, number of shocks prior to EMS arrival and number of shocks prior to randomization, treatment allocation, electrode placement for each defibrillation, number of defibrillations before DSD, ROSC and if the patients survived the event. Furthermore, if the patient has a known identity, personal id-number will be included to enable follow up. If the patients do not have a known identity a temporary identification number will be used.

The prehospital CRF allows for real-time monitoring of randomization and allows for early start of follow-up.

Other core resuscitation characteristics will later be reported and collected from the SRCR part 1 and ambulance charts. This registry data is standard and mandatory for all EMS personal to report and contains resuscitation and patient characteristics and reporting to the register is part of routine documentation.

ECG files from defibrillators. All data stored in the defibrillators after each use in the trial will be exported to a secure server and analyzed for defibrillation safety and CPR quality.

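### The target that more than 80% of the DSD arm receive DSD has two different denominators, so the same data can meet one and miss the other

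*Protocol*

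**What the plan says.** The Synopsis (Study endpoints, Feasibility) lists among the primary endpoints: "Among patients randomized to DSD, proportion that received DSD (target > 80" percent. Section 6.2.1 (Primary endpoints, Feasibility) lists the same item with the same threshold but a narrower base: "Among patients randomized to DSD still in VF in the following rhythm analysis, proportion that received DSD (target > 80" percent. Both are current text of version 1.1, and nothing in the Protocol says which one governs.

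The intervention is conditional on rhythm. The Synopsis describes "double sequential defibrillation in the following rhythm analysis phase if the patient is still in VT/VF". Section 2.2, on performing DSD in the trial, says "If the patient has VT/VF at the subsequent rhythm analysis (every two minutes during CPR) both defibrillators are charged simultaneously during chest compressions". Section 6.6 (Intervention) adds "All consecutive defibrillations will thereafter be performed with the DSD strategy until ROSC".

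Section 6.3.3 plans 40 patients, 30 of them allocated to DSD. Section 7.1 makes intention to treat the principal analysis set. Section 7.4 states that no hypothesis will be tested.

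The population is also described in two ways. Section 5.2.1 refers to "OHCA patients who remain in VT/VF after the first shock", and section 6.1 to "All adult OHCA patients (≥18 years) with VT/VF at rhythm analysis after the first defibrillation". The inclusion criterion in section 6.3.1 asks for VT/VF after ambulance arrival and at least one A-L shock, and does not clearly require VT/VF to persist after that shock. The Synopsis contains both kinds of wording.

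**The concern.** Section 6.6 places screening and randomisation after a shock, once compressions have resumed. A patient can therefore be out of VT/VF by the next analysis and not be due for DSD. The crew has then followed the plan, yet the Synopsis counts the case as DSD not received. Section 6.2.1 removes the same case from the calculation. The Synopsis figure thus mixes crew adherence with early rhythm conversion, which is not an adherence failure.

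Section 6.2.1 has a gap of its own. It says VF where the intervention text says VT/VF, so a patient in pulseless VT at that analysis is due for DSD but, read literally, falls outside the denominator.

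Neither version says whether DSD must be given at that analysis or may be given at any later shock. This matters for a patient who converts, refibrillates and then receives DSD: a success under the Synopsis, outside the denominator under section 6.2.1.

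Adherence to protocol is one of the stated purposes of the pilot, and its results are meant to shape the main trial. In an open-label study, a target with two definitions can be settled after the data are known.

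**Working it through.** **Inputs from the Protocol.** 40 patients at 3:1 give 40 × 3/4 = 30 DSD and 40 × 1/4 = 10 standard, which matches section 6.3.3. The target is strictly above 80% in both places.

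**Inputs not in the Protocol.** The share of the DSD arm out of VT/VF at the next analysis, the share of those who later refibrillate and receive DSD, and the delivery rate when DSD is due. These are assumed below and shown over a range.

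**Step 1: counts needed.** Let k be the number not in VT/VF at the next analysis and m = 30 − k. The smallest x with x/m > 0.80 is 25 of 30, 24 of 29, 22 of 27 and 20 of 24. For the full arm, 24/30 = 80.0% does not exceed 80%, so the Synopsis always needs 25.

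**Step 2: counts that split the result, with no later DSD among converters.**

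| k | m | Needed under 6.2.1 | Needed under Synopsis | Meets 6.2.1, misses Synopsis |
|---|---|---|---|---|
| 1 | 29 | 24 (82.8%) | 25 | 24 |
| 3 | 27 | 22 (81.5%) | 25 | 22 to 24 |
| 6 | 24 | 20 (83.3%) | 25 | 20 to 24 |

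The highest possible Synopsis figure is (30 − k)/30. At k = 6 it is 24/30 = 80.0%, so the target cannot be met even if all 24 patients due for DSD receive it.

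**Step 3: the reverse direction.** Suppose k = 6 and 19 of the 24 receive DSD: 19/24 = 79.2%, a miss under section 6.2.1. If all six converters refibrillate and receive DSD, the Synopsis gives (19 + 6)/30 = 83.3%, which meets the target. This assumes that such patients receive DSD on refibrillation.

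**Step 4: illustrative probabilities.** Let c be the conversion share, r the share of converters who refibrillate to a rhythm for which DSD is due, and 0.95 the delivery rate whenever DSD is due.

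- Synopsis: P(X ≥ 25), with X ~ Binomial(30, 0.95 × [(1 − c) + c·r]). For c = 0.2 and r = 0, the success probability is 0.95 × 0.8 = 0.76 and P(X ≥ 25) = 0.240.
- Section 6.2.1: m ~ Binomial(30, 1 − c), x ~ Binomial(m, 0.95), and the probability that x/m > 0.80.

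| c | Synopsis, r = 0 | Synopsis, r = 0.5 | Synopsis, r = 1 | Section 6.2.1 |
|---|---|---|---|---|
| 10% | 0.738 | 0.934 | 0.997 | 0.997 |
| 20% | 0.240 | 0.738 | 0.997 | 0.995 |
| 30% | 0.034 | 0.469 | 0.997 | 0.992 |
| 40% | 0.002 | 0.240 | 0.997 | 0.987 |

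At c = 5% and r = 0 the probabilities are 0.934 (Synopsis) and 0.997 (section 6.2.1), so the definitions nearly agree. With r = 0, the probability that the two results differ is 6% at c = 5%, 26% at 10%, 76% at 20%, 96% at 30% and 98% at 40%.

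**The case against.** The strongest reply is that little hangs on this item. Section 6.2.1 names a different main feasibility endpoint, the timing of randomisation, and that one is unaffected. No hypothesis is tested, no go/no-go rule is attached to the 80%, and both proportions could be reported side by side. This stands as a limit on severity. It does not remove the contradiction, because the Protocol lists the item as a primary endpoint and gives it a numerical target.

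The refibrillation argument is also weaker than the rest. Section 6.6 speaks of shocks that follow on and ends at ROSC. It does not expressly cover a patient who converts before any DSD and re-arrests. The reverse case and the r = 0.5 and r = 1 columns therefore rest on inference.

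The conversion, refibrillation and delivery rates are assumptions, and at low conversion the definitions almost coincide. The arm size of 30 is a goal, and stratified blocks do not guarantee it. The one-converter example needs only an arm of 30, and the contradiction itself needs none of these figures.

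The all-randomised proportion is a legitimate measure of exposure for planning a main trial. That is a reason to report it as a description, not to leave the target with two definitions.

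**Conclusion.** The concern holds and should be fixed. Two current statements of one primary feasibility target use different denominators, and the difference is substantive because DSD is conditional on rhythm. At the planned 30 patients, a single converter can split the result (24/29 = 82.8% against 24/30 = 80.0%). Six converters without later DSD put the Synopsis target out of reach whatever the crews do. How often the results would differ depends on conversion and refibrillation rates that the Protocol does not give: at 95% delivery and no refibrillation, the chance runs from 6% at 5% conversion to 98% at 40%.

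The effect is confined to the adherence target in the DSD arm. The timing endpoint and the comparisons between arms are untouched. The population wording is a separate, smaller inconsistency, but it bears on this one: it affects how many randomised patients can be out of VT/VF at the next analysis.

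**What to change.** - Use one denominator in the Synopsis and in section 6.2.1: patients randomised to DSD who are in VT/VF at the first rhythm analysis after randomisation. Correct the Synopsis line and change VF to VT/VF in section 6.2.1.
- State whether DSD counts as received only at that analysis or also at a later shock.
- Report, by arm, the number not in VT/VF at that analysis. The proportion among all randomised to DSD can be given as a description of exposure, without the target.
- Use this subset only for the adherence target. It is defined after randomisation and should not be used to compare arms. The ITT and mITT sets in section 7.1 stay as they are.
- Separately, reconcile the population wording in the Synopsis and sections 5.2.1, 6.1 and 6.3.1.

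The cost is mainly wording. The rhythm should be readable from the device files, since "All data stored in the defibrillators after each use in the trial will be exported to a secure server". Finding the first analysis after randomisation also requires placing randomisation on that record. The CRF1 items listed in section 8.1 include shocks before randomisation but do not name its time, and the form's own time stamp is made after care has ended. If the time is not captured elsewhere, one CRF1 item is needed. The statistical price is a smaller denominator and a wider interval.

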#### Safety:

- Major adverse events (e.g. defibrillator malfunction)
- Chest compression fraction (hands off time during CPR, target > 80% in both groups)

#### Secondary endpoint:

- Proportion of patients with sustained return of spontaneous circulation (ROSC) at hospital arrival
- Total number of defibrillations to sustained ROSC

#### Tertiary Outcomes:

- Survival to hospital admission
- Survival to hospital discharge
- Survival at 30 days
- Neurological function (mRS and CPC) at 30 days
- Neurological function (mRS and CPC) and Health-related Quality of life at 90 and 180 days

Planned duration of the clinical investigation:

Q2 2024 - Q4 2025

# 2. Identification and description of the investigational device

## 2.1. Description of the investigational device

Corpuls3 and Corpuls1 are defibrillators with capabilities of monitoring of cardiac rhythm and vital functions but also defibrillation, cardioversion and pacing and are part of the standard equipment in the EMS units in the participating sites.

Corpuls3 is a portable device with a modular structure which can be used as a defibrillator/monitor or as a full patient monitor in its own right.

The risk classification of Corpuls3 and Corpuls1 are non-invasive IIb

Version No: 1.1

Date: 2024-10-27 13 (48)

Image: Corpuls3

The corpuls3 provides monitoring of cardiac rhythm and vital functions, diagnostic and therapeutic functions for treatment of emergency and intensive-care patients. A 12 lead ECG function allows the user a comprehensive ECG diagnosis, which can be optionally supplemented by ECG analysis software.

[figure not shown]
Further monitoring functions include oxygen saturation measurement (pulse oximetry), carbon dioxide measurement (capnometry) and temperature measurement, in addition to non-invasive and invasive blood pressure monitoring. Corpuls3 provides the following therapeutic functions:

- defibrillation
- cardioversion
- pacing

Defibrillation with corpuls3 is performed with a Biphasic, positive rectangular waveform 4 msec. (90 % energy) and a negative rectangular waveform 3 msec. (10 % energy) pulse.

Version No: 1.1

Date: 2024-10-27 14 (48)

The defibrillator which operates with the corpuls 3-specific biphasic pulse has two operating modes:

- automatic external defibrillation (AED mode)
- manual defibrillation and cardioversion (manual mode)

In AED mode, the user is assisted by an automated ECG analysis, verbal instructions (configurable) and a metronome (configurable). The defibrillation pulse is triggered by the user.

In manual defibrillation mode, the user has full freedom of action and decision-making. Defibrillation is performed by applying disposable adhesive electrodes, so-called corPatch electrodes.

The standard position of the corPatch electrodes is the A-L Position, but alternative electrode positioning, including A-P should be considered in refractory VF since 2015.

[figure not shown]

Image Anteriolatal (standard) corpatch electrode placement from corpuls3 user manual

Version No: 1.1

Date: 2024-10-27 15 (48)

The corpuls1 is a defibrillator/patient monitoring system/externalpacer and is intended for the following purposes for the treatment of emergency- and intensive-care patients:

- Monitoring patients.
- Measuring vital parameters.
- Performing defibrillations and cardioversions on adults, children and neonates.
- Performing external pacer therapy (option).
- Check the quality of thorax compressions in cardiopulmonary resuscitation (optional).
   The following therapy functions are available:
- Defibrillation (AED mode, manual mode)
- Cardioversion
- External pacer therapy (option)

Image: Corpuls1

The corpuls3 and corpuls1 are intended for measurement and monitoring of vital functions in addition to defibrillation, cardioversion or cardiac pacing of patients in the preclinical and clinical field by qualified medical staff trained in the use of the device.

Version No: 1.1

Date: 2024-10-27 16 (48)

Corpuls3 and Corpuls1 may only be operated by trained medical staff of for example hospitals, doctor's offices and emergency medical services, as well as of authorities and public safety organizations.

The qualified staff must be

- trained in proper handling, use and operation of the device and of the approved accessories as well as be
- trained in basic and advanced resuscitator measures (Basic Life Support and Advanced Cardiac Life Support).

For further information please see attached Description and intended purpose Corpuls3 and Corpuls1

